### **Inclusion/exclusion criteria for patients and donors**

#### **Participant inclusion criteria**

- Age 18 years or older.
- Able to provide informed consent.
- Willing and able to comply with all the required study procedures.
- Must have at least one of the following conditions
  - Underlying inflammatory bowel disease (ulcerative colitis, Crohn's disease), or microscopic colitis diagnosed by a gastroenterologist
  - Irritable bowel syndrome as defined by Rome IV diagnostic criteria\*:
    - Recurrent abdominal pain or discomfort\*\* at least 3 days/month in last 3 months associated with two or more of the following:
      - Improvement with defecation
      - Onset associated with a change in frequency of stool
      - Onset associated with a change in form (appearance) of stool
- \* Criterion fulfilled for the last 3 months with symptom onset at least 6 months prior to diagnosis
- \*\* “Discomfort” means an uncomfortable sensation not described as pain.
- Chronic severe constipation/dysbiosis as diagnosed by a gastroenterologist
- Colonized with ARO based on positive rectal cultures for same organism on 2 separate occasions (each culture 1 month apart) and must have a positive culture within 14 days of enrollment.

#### **Participant exclusion criteria**

- Planned or actively taking another investigational product
- Patients with neutropenia with absolute neutrophil count  $<0.5 \times 10^9/L$
- Evidence of toxic megacolon or gastrointestinal perforation on abdominal x-ray
- Peripheral white blood cell count  $> 30.0 \times 10^9/L$  AND temperature  $> 38.0^{\circ}C$
- Active gastroenteritis due to *Salmonella*, *Shigella*, shiga toxin-producing *E. coli*, *Yersinia* or *Campylobacter*.
- Unable to tolerate FMT or enema for any reason.
- Requiring systemic antibiotic therapy at the time of FMT.
- Actively taking *Saccharomyces boulardii* or other probiotic; yogurt is allowed
- Severe underlying disease such that the patient is not expected to survive for at least 30 days.
- History of severe allergy to any food

### **Donor inclusion**

- Able to provide and sign informed consent.
- Able to complete and sign the donor questionnaire
- Able to adhere to fecal transplantation stool collection standard operating procedure.

### **Donor exclusion**

- Tested positive for any of the following: Human Immunodeficiency virus (HIV) 1/2, hepatitis IgM, hepatitis B (HBsAg), hepatitis C antibody, syphilis, human T-lymphotrophic virus (HTLV) 1/II and COVID-19 Detection of vancomycin resistant *Enterococcus* (VRE), methicillin resistant *S. aureus* (MRSA), Extended-spectrum beta-lactamase (ESBL) or carbapenem-resistant enterobacteriaceae (CRE); *Salmonella*, *Shigella*, shiga toxin-producing *E. coli*, *Yersinia* and *Campylobacter*, ova, parasites, *C. difficile* toxin, norovirus, adenovirus, rotavirus on stool examination
- Physical contact with COVID-19 positive individual within 14 days of stool donation
- History of any type of active cancer or autoimmune disease
- History of risk factors for acquisition of antibiotic resistant organisms (MRSA, VRE, ESBL, CRE) HIV, syphilis, Hepatitis B, Hepatitis C, prion or any neurological disease as determined by the donor questionnaire, appendix A.
- History of gastrointestinal comorbidites, e.g., inflammatory bowel disease, irritable bowel syndrome, chronic constipation or diarrhea
- Receipt of blood transfusion from a country other than Canada in preceding 6 months
- Antibiotic use or any systemic immunosuppressive agents in the 3 months prior to stool donation
- Receipt of any type of live vaccine within 3 months prior to stool donation
- \*(participant with history of severe allergy to any food is excluded)History of depression, anxiety or panic disorder
- History of any type of active cancer or autoimmune disease
- Body mass index > 29
- Failed any one of the donor screening questionnaire at the time of donor screening
- Any current or previous medical or psychosocial condition or behaviours which in the opinion of the investigator may pose risk to the recipients or the donor

### **Adverse Event Reporting**

All adverse drug event (ADE) and serious adverse events (SAE) will be tracked in the participant's study file and REDCap and reported to Island Health's Clinical Research Ethics Board (CREB). As per Health Canada, a SAE is defined as "an adverse drug reaction that requires inpatient hospitalization or prolongation of existing hospitalization, that causes congenital malformation, that results in persistent or significant disability or incapacity, that is life threatening or that results in death". Each SAE that is attributed to FMT is subject to expedited reporting to Health Canada and should be reported individually in accordance with the data element(s) specified in the Health Canada/ICH Guidance Document E2A: "Clinical Safety Data Management: Definitions and Standards for Expedited Reporting". Expedited reports are required for events that meet all of these three criteria: serious, unexpected and a suspected causal relationship; this is defined as any untoward medical occurrence that at any dose results in

any one of the following: results in death; is life-threatening; requires inpatient hospitalization or prolongation of existing hospitalisation; results in persistent or significant disability/incapacity or is a congenital anomaly/birth defect. An event reaction causality scoring system will be used to determine the probability of the relationship of the event to study intervention. Source documents will be used to capture AEs and SAEs. All AEs will be reported to the CREB within 24 hours of the PI being aware of the event.

Known side effects of FMT are described in table 6.0; these potential effects are listed in the informed consent and participants are advised to report these and any other effects that they feel is relevant or causing concern.

### **FMT Side Effects**

Possible FMT Side Effects	Frequency that the side effect has been reported
Hard stool	10%
Increase in flatulence or passing gas	10%
Stomach discomfort	8%
Increase appetite	3%
Nausea	2%
Minor temporary pressure or discomfort in the rectum	1%

There has been a report of transmission of multi-drug resistant organism (MDRO) to patients who received FMT from a donor, whose stool was not screened for the MDRO.

There may be a small risk of transmission and infection due to MDRO. However, the donor's stool samples used at Vancouver Island Health Authority routinely undergo screening for MDRO. The donor's blood and stool are regularly tested for transmissible infectious organisms that may cause disease. If a donor and/or their stool sample shows abnormal result(s), such stool samples will not be considered for FMT processing.

### **Proposed sample size and the justification for the assumptions**

Fifty participants will be recruited for the chronic GI dysbiosis component of the study based on the 5% response in placebo group and 24% in FMT arm with significance level 5% and power of 80% in the FMT trial of ulcerative colitis. For the ARO participants, the sample size will be 20 as this will be a pilot project to determine the feasibility of further study.

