### **Primary Outcome Measurements:**

For the participants with chronic GI dysbiosis, the efficacy of FMT treatment will be based on improvement in participant's symptom score from baseline (pre-transplant) to intervention (post-transplant) 4 weeks, 12 weeks and 1 year following FMT. For participants with ARO colonization, determination of clearance of ARO based on stool culture for ARO at baseline, day 7, day 30 and 3 months following last FMT.

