### **Secondary Outcome Measurements for participants with IBD, MC or IBS:**

1. Evaluate efficacy and safety of FMT in patients with chronic gastronintestinal dysbiosis and antimicrobial resistant organism in the gut

2. Evaluate the Ulcerative Colitis Disease Activity Index from baseline and following each FMT using partial-MAYO score.
3. Evaluate Crohn's Diseases Activity Index (CDAI) change from baseline 4 weeks, 12 weeks and 1 year post-FMT.
4. Evaluate Microscopic colitis response to FMT using physician's global assessment and number of unformed bowel movements per 24 hours
5. Evaluate Irritable Bowel Syndrome Severity Scoring System (IBS-SSS) grade assessment change from baseline, 4 weeks, 12 weeks and 1 year post-FMT.

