## **The Proposed Trial**

### **The proposed design of the study**

The design of this research is a prospective open-label trial using lyophilized or frozen FMT to evaluate efficacy of fecal microbiota transplantation for treatment of chronic gastrointestinal (GI) dysbiosis and clearance of antimicrobial resistant organism (ARO) from the GI tract of the ARO colonized individuals.

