### **The planned trial interventions**

#### **Recruitment**

The research coordinator will be responsible for coordinating the recruitment, screening of potential participants using the inclusion/exclusion criteria and reviewing with the PI. The PI will make the final determination of a potential participants' eligibility. Fifty participants with chronic GI dysbiosis will be recruited. Twenty patients with confirmed ARO will be recruited to take part in this study; the ARO study results will be used to determine the feasibility of further study.

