## GI Dysbiosis Participants

Following informed consent and pre-transplant, enrolled participants will have their blood collected for Hepatitis BsAg, Hepatitis C Ab, HIV, Syphilis serologies unless these serologies were performed within 3 months of enrollment. Blood is collected for these pathogens to determine their serostatus at the time of study enrollment and prior to receiving FMT.

All participants will be assessed at day 1 by the physician-investigator. A medical history and physical examination will be performed. In addition, optional blood and stool samples may be collected from IBD/IBS participants who consented for these samples prior to the FMT and at weeks 4, 12 and 6 months from FMT.

The participants will receive lyophilized FMT (LYO-FMT) or frozen FMT enemas using stool collected from healthy, screened donor(s). Participants will receive FMT treatment via retention enema(s) twice weekly for 4 weeks. If there is symptom improvement after 4 weeks of treatment, then the participants will receive FMT treatment once weekly for 4 additional weeks. If the participant does not experience symptom improvement after the initial 4 weeks of treatment, the physician-investigator will discuss options with the participant and a mutual decision will be reached to pursue an additional 4 weeks of FMT treatment or withdraw from the study and pursue usual care. When continued improvement is seen then the participants will receive FMT maintenance; the frequency of FMT treatment is participant dependent and is at the discretion of the physician-investigator and is based upon clinical exam and symptomatic improvement. If no improvement is seen after the 8th FMT, then the participant will be withdrawn from the study and s/he reverts to usual care for his/her condition. Participants can opt to receive maintenance FMT in the clinic or be trained by study staff for home administration.

At the time of each study visit and follow up, participants will be assessed for clinical response, including bowel movements and adverse reactions. Any participant who reports worsening symptoms or AE/SAE will return to the clinic for assessment by the physician investigator. At that time, the participant will undergo a physical exam. Additional tests may be ordered (i.e. blood work) at the discretion of the treating physician investigator.

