### **The proposed type of statistical analyses**

The clinical response rate will be determined using standard binary outcome protocols. Also, logistic regression and survival analysis methods will be performed. The primary endpoints of clinical response, and treatment failure will be analyzed by logistical regression.

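### The 50 dysbiosis participants are justified by a two-arm placebo comparison from a UC trial, but this trial is a single open-label group, so the 80% power is tied to no analysis planned here

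*Combined protocol and SAP*

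**What the plan says.** The section on proposed sample size gives one rationale for the dysbiosis component: "5% response in placebo group and 24% in FMT arm with significance level 5% and power of 80% in the FMT trial of ulcerative colitis". It states no formula, sidedness, allocation ratio or dropout allowance. The same section sizes the ARO component at 20 as a pilot; it does not use that label for the dysbiosis component.

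The rest of the protocol describes a different kind of study:

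- **Design.** "The design of this research is a prospective open-label trial using lyophilized or frozen FMT". No placebo or control arm and no randomisation is described.
- **Recruitment.** "Fifty participants with chronic GI dysbiosis will be recruited", as one group.
- **Treatment.** Under GI Dysbiosis Participants, everyone receives FMT enemas, lyophilized or frozen. The two preparations are not set up as a randomised or planned comparison.
- **Primary outcome.** Improvement in "symptom score from baseline (pre-transplant) to intervention (post-transplant) 4 weeks, 12 weeks and 1 year following FMT", a within-participant comparison with baseline.
- **Analysis.** "The primary endpoints of clinical response, and treatment failure will be analyzed by logistical regression". Survival methods and a response rate are also mentioned, but no comparator, null rate or benchmark.

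**The concern.** A sample-size statement should show what the planned analysis can deliver with the planned number. Here the power statement refers to a contrast between FMT and placebo, and the trial contains no placebo group.

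The sentence can be taken in two ways. If it claims 80% power for this trial, the power belongs to a comparison that the trial does not make. If it only reports the design of the earlier UC trial, this trial has no power or precision statement of its own. The section needs rewriting either way.

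This is the only rationale for the size of the efficacy component. A reader could take it to mean that the trial has 80% power to show benefit over placebo, when 50 treated participants can give only an uncontrolled response proportion or a change from baseline. The plan states the precision of neither.

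**Working it through.** **Inputs.** From the sample-size section: response 5% (placebo) and 24% (FMT), significance level 5%, power 80%, n = 50. Assumptions, because the documents are silent: 1:1 allocation and a two-sided test.

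**1. Reproducing the figure of 50.** Two proportions, normal approximation, unpooled variance:

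n per arm = (1.960 + 0.842)² × (0.05×0.95 + 0.24×0.76) / (0.24 − 0.05)²
= 7.849 × (0.0475 + 0.1824) / 0.0361
= 7.849 × 0.2299 / 0.0361 = 49.98, so **50 per arm, 100 in total**.

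With pooled variance under the null (mean rate 0.145):

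n per arm = [1.960 × √(2×0.145×0.855) + 0.842 × √0.2299]² / 0.0361 = 52.71, so 53 per arm.

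The stated inputs thus reproduce 50 as the size of one arm of a two-arm trial. No variant tried gives 50 as a two-arm total: the smallest per-arm figure (arcsine, one-sided 5%) is 37.67, which rounds up to 38 per arm and 2 × 38 = 76 in total.

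**2. Is there a planned analysis to which the 80% could belong?**

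| Candidate analysis | In the plan? | Power with 50 |
|---|---|---|
| FMT against concurrent placebo, 5% vs 24% | No; there is no placebo arm | 80% would need 50 per arm |
| One group against a fixed 5% rate | No; no null rate is named | 97% to 99% at 24% (step 3) |
| Change in symptom score from baseline | Yes | Cannot be computed; no expected change or SD is given |
| Logistic regression of response and treatment failure | Yes | Cannot be computed; no comparator or covariate is named |

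**3. One group of 50 against a fixed 5%.** Exact binomial, X out of 50:

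- Success at X ≥ 6: P(X ≥ 6 given 5%) = 0.038; P(X ≥ 6 given 24%) = 0.989.
- Success at X ≥ 7: P(X ≥ 7 given 5%) = 0.012; P(X ≥ 7 given 24%) = 0.972.

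These are one-sided. On this reading 50 is ample, but the power is not 80%.

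**4. What one group of 50 does give.** Exact (Clopper-Pearson) 95% limits for x responders: lower = Beta(0.025; x, 51 − x), upper = Beta(0.975; x + 1, 50 − x).

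- 12/50 = 24%: 0.131 to 0.382, or 13% to 38%.
- 25/50 = 50%: 0.355 to 0.645 (0.3553 to 0.6447 before rounding), or 36% to 64%. This is the widest interval for any x out of 50, with width 0.289.

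**The case against.** **The 5% may be meant as a historical benchmark.** In an uncontrolled trial that is a natural use of a placebo rate from elsewhere, and it makes 50 look generous. What stands is that the number 50 is not discredited. What does not stand is the justification. No section states such a test, it would not give 80%, and the 5% comes from UC patients on placebo, while the inclusion criteria also admit Crohn's disease, microscopic colitis, IBS and chronic severe constipation/dysbiosis.

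**The text attributes the 80% to the earlier UC trial, and the design is openly described as open-label.** This is fair, and it makes misreading less likely. It leaves this trial with no power or precision statement of its own.

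**Stronger readings that the documents do not support.**

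- A reader might infer that the trial is underpowered, for example by splitting the 50 into two groups of 25. Nobody proposed that design, and step 3 points the other way.
- A reader might infer an arithmetic error. The inputs do reproduce 50, per arm. That a per-arm size was carried over as the whole sample is a likely explanation, but an inferred one, since no formula is shown.
- A reader might infer that the planned analyses are known not to have 80% power. Power for the change in symptom score cannot be computed in either direction.

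**Endpoint definitions are a different matter.** The choice among the three primary time points and the responder definitions by disease need attention however the 50 is justified. They are separate points and are not counted here.

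**Conclusion.** The concern holds as a mismatch between justification and design. The 5% vs 24% calculation with 80% power describes a two-arm placebo-controlled trial; this is one treated group compared with baseline, and the documents tie the 80% to no analysis planned here. The stated inputs correspond to 50 per arm by the unpooled two-sided formula and 53 by the pooled one, assuming 1:1 allocation.

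It should be fixed, but it calls for no change in recruitment and does not show that 50 is too few. The absence of a control group is clear from the design, recruitment, treatment and analysis sections. How 50 was reached is inference, and the single-arm power figures are for a test outside the plan.

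**What to change.** Keep 50. In the sample-size section, delete the 5% vs 24%, 80% power justification and replace it with a precision statement, for example:

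> *The dysbiosis component is a single-arm sample of 50 with no placebo comparison. The response proportion will be reported with an exact 95% confidence interval. All treated participants are in the denominator, and anyone without an observed response, for whatever reason, counts as a non-responder. For illustration, 12/50 responders gives 13% to 38%; the widest interval, at 25/50, is 36% to 64%.*

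The 24% in this text is illustrative only, since it is a UC figure. If a single-arm test is wanted, pre-specify a null rate and a success threshold justified for the mixed cohort, rather than carrying over the UC placebo 5%.

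One related passage needs the sponsor's attention. Under GI Dysbiosis Participants, twice-weekly treatment for 4 weeks reaches 2 × 4 = 8 administrations at the end of week 4. For a participant without improvement at that point, the section allows a joint decision to continue, yet it also says: "If no improvement is seen after the 8th FMT, then the participant will be withdrawn from the study". The sponsor must reconcile these statements. The denominator above covers every treated participant whichever way that is done.

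**Cost.** No extra patients and no change to treatment. The stated inference becomes an uncontrolled proportion with a wide interval, and the all-treated denominator can lower the reported rate.

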### **The proposed type of statistical analyses**

The clinical response rate will be determined using standard binary outcome protocols. Also, logistic regression and survival analysis methods will be performed. The primary endpoints of clinical response, and treatment failure will be analyzed by logistical regression.

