## **Study Objectives and Outcome Measures**

The objective of this study is to assess the efficacy of FMTs via enema for 1) symptom improvement in individuals with a formal diagnosis of dysbiosis due to active inflammatory bowel disease (CD, UC), microscopic colitis or irritable bowel syndrome; 2) clearance of antimicrobial resistant organism from the gastronintestinal tract.

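### One clinical response rate is named for 50 participants with any of five conditions, and none by diagnosis; if response differs between conditions, the result depends on the enrolment mix

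*Combined protocol and SAP*

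**What the plan says.** All references are to the combined protocol and SAP.

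- **Who enters.** *Recruitment* treats the dysbiosis participants as one block: "Fifty participants with chronic GI dysbiosis will be recruited". *Participant inclusion criteria* admits them on the rule "Must have at least one of the following conditions". Leaving aside the separate group colonized with resistant organisms, the list covers UC, CD, MC, IBS and chronic severe constipation/dysbiosis. No quota, cap, minimum or stratum is given.
- **What the trial asks.** *Study Objectives and Outcome Measures* aims at symptom improvement in "dysbiosis due to active inflammatory bowel disease (CD, UC), microscopic colitis or irritable bowel syndrome".
- **How it was sized.** *Proposed sample size and the justification for the assumptions* sets the 50 "based on the 5% response in placebo group and 24% in FMT arm", at a 5% significance level and 80% power, and gives the source as "in the FMT trial of ulcerative colitis".
- **What is measured.** The primary outcome is improvement in the participant's symptom score at 4 weeks, 12 weeks and 1 year. The instruments are partial Mayo (UC), CDAI (CD), physician's global assessment with a count of unformed stools (MC) and IBS-SSS (IBS). None is named for constipation/dysbiosis. Only the CD section defines clinical response numerically: a CDAI below 150, or a fall of at least 100 points.
- **How it is analysed.** *The proposed type of statistical analyses* says "The clinical response rate will be determined using standard binary outcome protocols". It also mentions survival methods and a logistic regression for response and treatment failure. It names no covariate and no analysis by diagnosis.

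**The concern.** A response on a 9-point colitis index, a 100-point fall in CDAI and an improvement on a 500-point IBS scale are different events. They may occur at different rates, whether because the treatment works differently, because background improvement differs, or because the bar for response is set differently. In any of these cases a single rate over all 50 is a weighted average, and the weights are whatever recruitment delivers.

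Two things are at stake. The same effect in each disease could give quite different headline figures under different enrolment. And a reader could take a respectable overall rate as support for every named disease when one of them hardly responded. The objective names the diseases, and one overall figure cannot answer for any one of them.

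**Working it through.** **1. Reproduce the plan's 50.** Inputs from the sample-size section: 5%, 24%, significance level 5% (taken as two-sided, since sidedness is not stated), power 80%. For two independent proportions with unpooled variance:

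n = (1.960 + 0.842)² × [0.05 × 0.95 + 0.24 × 0.76] / (0.24 − 0.05)² = 7.849 × 0.2299 / 0.0361 = 49.98, so 50 per arm.

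The figure therefore reproduces as one arm of a two-arm UC comparison. The design section describes an open-label trial with no comparator, and nothing in the calculation refers to CD, MC, IBS or constipation.

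**2. How far the overall rate moves with case mix.** Let s be the share of UC among the 50 and q the response rate in all other conditions. Overall rate = 0.24s + q(1 − s). The 24% is the plan's. The documents give no rate outside UC, so q is an assumption shown over a range.

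| Assumed q | s = 0.8 | s = 0.2 |
|---|---|---|
| 50% | 0.192 + 0.100 = 29.2% | 0.048 + 0.400 = 44.8% |
| 10% | 0.192 + 0.020 = 21.2% | 0.048 + 0.080 = 12.8% |
| 24% | 24% | 24% |

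**3. Can a conclusion change?** The plan states no test against a fixed rate. As an illustration, take its 5% placebo figure as a benchmark: 6 of 50 responders is the exact one-sided 5% cut-off (actual level 0.038). Assume that every non-UC condition responds at only 5%.

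| UC participants of 50 | Overall rate | Chance of at least 6 responders |
|---|---|---|
| 35 | (35 × 0.24 + 15 × 0.05)/50 = 18.3% | 0.92 |
| 13 | (13 × 0.24 + 37 × 0.05)/50 = 9.9% | 0.38 |
| 5 | (5 × 0.24 + 45 × 0.05)/50 = 6.9% | 0.12 |

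The first row shows masking: an overall 18.3% with the other conditions no better than the benchmark. The dependence fades when the other rates are high. With CD at 30%, MC at 40% and IBS at 50% (all assumed), the overall rate is 28.8% with 35 UC participants and 5 in each other condition, and 44.4% with 35 IBS participants and 5 in each other condition. The chance of at least 6 responders exceeds 0.99 in both.

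**4. What by-diagnosis reporting can deliver.** Exact (Clopper-Pearson) two-sided 95% intervals run from the 0.025 quantile of Beta(x, n − x + 1) to the 0.975 quantile of Beta(x + 1, n − x):

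- 12/50: 13.1% to 38.2%
- 3/12 (about an even four-way split): 5.5% to 57.2%
- 2/10 (an even five-way split): 2.5% to 55.6%

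**The case against.** The strongest reply has five parts.

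- **Pooling is not stated.** The analysis section is three generic sentences and never says that diagnoses are combined. That stands: pooling is inferred from the singular rate, the single number of 50 and the absence of any analysis by diagnosis. It is the natural reading, and if the sponsor means otherwise, the text needs to say so.
- **Case mix need not matter.** A reader might infer that the overall rate shifts with enrolment whatever happens. The documents do not support this. With equal rates and comparable definitions it does not move, and the size of any shift rests on assumed rates.
- **Disease-level assessment is planned.** A reader might infer that the diseases are ignored, or appear only as secondary outcomes. That goes too far. The primary outcome is a symptom score, which in practice means the disease instruments, and the UC section ties efficacy to partial Mayo at the same time points. What is missing is a response rate by diagnosis, and a definition of response outside CD. The UC and IBS sections give severity bands (for UC, including a remission band), and the MC section gives no cut-off.
- **A joint summary is legitimate.** The objective is framed around dysbiosis as a common target, and an open-label study may report an overall figure. That stands, so the overall rate should stay, with limits on what is concluded from it.
- **The strata are small.** True, but the wide intervals show what 50 participants can say about each disease, and one overall rate conceals that.

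A reader might also infer that the trial is underpowered overall. If 24% held in every condition, 50 participants tested against a fixed 5% would have power of about 0.97 to 0.99. The weakness is in interpretation and in precision by diagnosis.

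**Conclusion.** The point holds in conditional form. As naturally read, the plan gives one response rate for a group of up to five conditions in no fixed proportion, with sizing rates borrowed from UC and a numeric response definition for CD alone. If rates or definitions differ between conditions, the overall figure depends on enrolment. In the range examined, moving UC from 80% to 20% of the group shifts it by about 16 points upward (others assumed at 50%) or 8 points downward (others assumed at 10%), and by nothing if all conditions share one rate. The only rate taken from the documents is 24% for UC. The missing by-diagnosis rates and response definitions are matters of record and do not depend on these assumptions.

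**What to change.** In *The proposed type of statistical analyses*:

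- Report the response rate by index diagnosis for all five eligible conditions, each with an exact two-sided 95% confidence interval. Fix one index diagnosis per participant before the first FMT, since entry allows more than one condition.
- Set a response definition for each condition before the data are analysed, based on the instruments already collected, and state a measure for constipation/dysbiosis.
- Show the overall rate beside the case mix, and draw no disease-specific efficacy conclusion from it.

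In *Proposed sample size and the justification for the assumptions*, state that the 5% and 24% rates and the 80% power refer to UC only and are not claimed for the mixed group or for any other condition.

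**Cost.** Recruitment and treatment do not change. Beyond the wording, the sponsor has to agree the missing response definitions and a measure for the fifth condition. The by-diagnosis intervals will be visibly wide, as shown above, and the 50 will no longer carry a power claim for the mixed group.
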